Improving Preterm Infant Outcomes with Family Integrated Care and Mobile Technology

ID: 16-19542

Study Protocol and Statistical Analysis Plan

January 17, 2018

Study Protocol

Study staff at UCSF, UCLA, BCH-O, and CRMC will perform the following procedures.

Usual FCC Group:

Education: Parents will receive an orientation to the unit by a NICU nurse and will have access to the usual written and video materials provided by the NICU. Parents will receive all NICU-required individualized parent teaching and support, delivered at the bedside by nurses or the Discharge Coordinator.

Direct care: Parents will be encouraged by nurses to participate in infant care under nursing supervision for feeding, bathing, dressing, and holding skin-to-skin.

Social work and other support: Individualized support from social workers, lactation consultants and other specialists will be offered.

Documentation: Parents will not be asked to formally document any observations of their infant or their own skills acquisition. Nurses and Discharge Coordinators will complete the standard Discharge Teaching Checklist per usual hospital policies. Parents will be asked to track their time in the NICU, time learning from nurses and time spent in infant caregiving activities, and to keep a journal of their NICU experience (without any specific instructions about content). They will use the We3Health App for this, with only the data tracking and journal features activated. These data will not be shared with the clinical team.

mFI-Care Group:

mFI-Care clinical team and alumni parent training: After completion of the usual FCC group enrollment, nurses who volunteer to provide care to mFI-Care infants/parents and the volunteer alumni parents will receive in-person and online training from the study team. The nurse training will follow the Canadian FI-Care curriculum and cover topics such as the differences between FCC and mFI-Care, psychological implications of preterm birth for parents, infant development, parent-infant attachment, re-conceptualization of the nursing role, and parent coaching skills. Alumni parent training will follow the Canadian FI-Care curriculum. Physicians, therapists and social workers will receive in-person and online inservice education specific to their roles. Once training and inservice education are complete, mFI-Care enrollment will commence.

Education: Parents will be oriented to the unit by a mFI-Care nurse who will introduce them to the program, explain the parent's role as primary caregiver for their infant, and orient them to the NICU and parent resources, including the We3Health App. Parents will be able to access the App in English. Parents will be provided the Canadian FI-Care Parent Education program, a 3-week rotating curriculum offered 3 afternoons per week (Appendix 2.B). The small group sessions will be facilitated by a member of the study team. Parents will participate in-person or access the content remotely at a time of their choosing via the We3Health App.

Direct care: mFI-Care parents will be treated as the infant's primary caregiver, with nurses serving as teachers and coaches. Parents will not be required to be in the NICU at specified hours as in the Canadian FI-Care program, but when in the NICU, they will be expected to provide as much infant care as they can, with support from mFI-Care-trained nurses. Parents will not provide ventilation management, intravenous fluid or intravenous medication administration.

Daily medical rounds: mFI-Care parents will be expected to participate in daily medical rounds either in-person or remotely by logging on to the HIPAA-compliant web-link via the We3Health App. Parents will report standardized data of their infant's status to the rounding care team, ask questions, and reach consensus with the clinicians on the infant's daily plan using the We3Health App. Nurses will provide role-modeling and coaching to prepare parents for this role.

Peer-Support: mFI-Care parents will receive peer support from alumni parents who will contact them remotely, by telephone, text or through the We3Health App, at least twice weekly and as desired. The

mFI-Care parents will also be able to ‘meet’ and share experiences and information with other mFI-Care parents through a secure online parent forum on the We3Health App.

Documentation: mFI-Care parents will be expected to document time spent with their infant and record infant activity, feeds and output using the We3Health App. They will also use the App to keep a journal of observations of their infant and their own NICU experience that they can share with family, friends and the clinical team if they wish. Parents will access the FI-Care skills checklist via the We3Health App and track their learning and skills acquisition. The infant observation data, parent-team communication and parent skills will be accessible to the clinical team and parents for rounds.

Parent Resources for both groups: All parents, regardless of group assignment, will be provided with similar resources to enable them to spend extended periods or stay overnight with their infant and to facilitate breastfeeding. Each single patient room in the study site provides a reclining chair, sofa bed, locked storage, wifi and a bedside tablet computer for parent use. There is also a nearby family lounge with kitchen, shower, and laundry facilities.

Statistical Analysis Plan:

Descriptive statistics will be provided for all study variables: means and standard deviations for quantitative variables and frequencies and percents for categorical variables. Data analysis will be based on an intention-to-treat strategy with all participants enrolled in the usual FCC or mFI-Care groups at UCSF analyzed within their respective groups regardless of compliance with the group assignment. Outcomes will be compared between the usual FCC and mFI-Care groups using t-tests for continuous variables, Wilcoxon tests for ordinal variables, and chi-square tests for categorical variables. We expect 225 eligible ICN admissions during the study period and anticipate enrolling 50 parent-infant pairs in each group (usual FCC and mFI-Care) at UCSF. Assuming 20% attrition, we will have complete data on 40 infants per group. Enrollment at the UCLA site is exploratory to further assess feasibility and acceptability thus statistical power is based on the UCSF sample. The primary outcome, change in weight Z-score, typically has a standard deviation of between 0.44-0.47 (data from Toronto pilot and Canada-led cRCT). With a 0.05 null-hypothesis rejection threshold (alpha) for the two-tailed t-test, we will have 80% power to identify a group difference of 0.28-0.29. Differences among the groups in potential confounding variables (e.g., GA, birth weight) will be examined. Variables that differ among the groups may be considered as covariates when examining group differences in the primary and secondary outcomes. The covariate-adjusted scores may provide more precise estimates of the effect sizes. We will calculate confidence intervals around the differences because this will give a better idea of the range of values around the true means for the population and guide the sampling strategy for the future US cRCT. We will compare participation rates in specific aspects of usual FCC and mFI-Care such as caregiving activities, education, time spent with the infant or holding skin-to-skin or the primary and secondary outcome variables to see if they differ for parents and infants with different characteristics (e.g., sex, race/ethnicity or distance between hospital and home). We will compare attitudes and perceived practices of nurses and physicians during the FCC and mFI-Care conditions.

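### Should staff training have waited until the last usual-care infant left the unit, rather than for the end of usual-care enrolment?

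*Combined protocol and SAP*

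**What the plan says.** The relevant text is the paragraph on clinical team and alumni parent training, under mFI-Care Group in the Study Protocol. It sets the order of events: "After completion of the usual FCC group enrollment, nurses who volunteer to provide care to mFI-Care infants/parents and the volunteer alumni parents will receive" training; then "Once training and inservice education are complete, mFI-Care enrollment will commence". Nurse training includes "re-conceptualization of the nursing role, and parent coaching skills". For other staff the text says "Physicians, therapists and social workers will receive in-person and online inservice education specific to their roles", with no separate start point.

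Control parents depend on the same workforce. Under Usual FCC Group, Education: "Parents will receive all NICU-required individualized parent teaching and support, delivered at the bedside by nurses or the Discharge Coordinator".

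Several provisions keep the conditions apart. Control parents use the app "with only the data tracking and journal features activated". The trained nurses are volunteers, and the Direct care paragraph ties them to the intervention families: "they will be expected to provide as much infant care as they can, with support from mFI-Care-trained nurses". Under Peer-Support, "mFI-Care parents will receive peer support from alumni parents who will contact them remotely". The group curriculum, reporting on rounds and the skills checklist are likewise described only for mFI-Care parents, and the section on parent resources describes single patient rooms.

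The Statistical Analysis Plan compares the groups by t-test under intention-to-treat at UCSF. It expects 225 eligible admissions, 50 pairs enrolled per group and 40 with complete data. It also compares staff attitudes and perceived practices between the two conditions.

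**The concern.** A sequential design protects controls from contamination only if control care has ended before staff learn the new approach. Here the trigger is the last enrolment, not the last departure. No passage requires a wash-out, and none bars a trained nurse from caring for a control infant still in the unit. Coaching skills are hard to set aside for one family, and intention-to-treat rightly keeps such infants in the control group. If mFI-Care is beneficial, the estimated difference is then too small, and the estimates are meant to inform a later cluster trial. The staff comparison would also be blurred if any control-condition measures were taken after training began; their timing is not stated.

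**Working it through.** **The plan's own figure.** Inputs from the Statistical Analysis Plan: SD 0.44-0.47, 40 per group, two-sided alpha 0.05, 80% power. The normal formula, SD × (1.960 + 0.842) × √(2/40), gives 0.276 and 0.294, which round to the stated 0.28-0.29. The exact t calculation gives 0.279 and 0.298. At a true 0.28 with SD 0.44, power by the t-test is 80.3%. The 95% CI half-width is t(0.975, 78) × 0.44 × √(2/40) = 0.196.

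**Dilution.** The documents give none of the following, so all are assumed: even enrolment over E = 26-52 weeks; S = 4-8 further weeks in the unit, with the outcome period equal to that stay; lag L = 0-4 weeks between the end of enrolment and trained practice; carry-over g, the share of the full effect that an exposed control receives.

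- Share of controls overlapping = (S − L)/E
- Mean share of their stay exposed = (S − L)/(2S)
- Dilution = product of these two × g
- Observed difference = 0.28 × (1 − dilution)

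Example with no lag, S = 8, E = 26, g = 25%: 0.308 × 0.5 × 0.25 = 0.0385, and 0.28 × (1 − 0.0385) = 0.269. About 31% of controls overlap, or 12 of 40. With S = 4, E = 52 it is 8%, or 3 of 40.

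Observed difference and power (true 0.28, SD 0.44, 40 per group):

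| Lag | Carry-over | S = 4, E = 52 | S = 8, E = 26 |
|---|---|---|---|
| 0 | 25% | 0.277; 79.5% | 0.269; 77.1% |
| 0 | 50% | 0.275; 78.7% | 0.258; 73.7% |
| 0 | 100% | 0.269; 77.1% | 0.237; 66.2% |
| 2 wk | 25% | 0.279; 80.1% | 0.274; 78.5% |
| 4 wk | 25% | 0.280; 80.3% | 0.277; 79.5% |

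At 25% carry-over without lag, the shift of 0.003-0.011 is 1-6% of the half-width (0.0027/0.196 to 0.0108/0.196). If mFI-Care has no effect there is nothing to dilute, so the type I error is untouched.

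**Cost of waiting.** Assume the 225 admissions arrive evenly over two equal phases (112.5 each) and the study end is fixed. Missed admissions = 225 × wait/(2E).

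- Wait of one average stay: 225 × 4/104 = 8.7 to 225 × 8/52 = 34.6. The share to be enrolled in the mFI-Care phase rises from 50/112.5 = 44% to 50/103.8 = 48% and 50/77.9 = 64%.
- Wait for the last infant, which is longer than an average stay. With 50 evenly spaced controls and gamma-distributed stays (assumed coefficient of variation 0.5), the mean wait is about 5.1 weeks (S = 4, E = 52) to 13.6 weeks (S = 8, E = 26). At 13.6 weeks, 225 × 13.6/52 = 59 admissions are missed and 50/53.6 = 93% of the rest must enrol.

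**Dropping late controls instead.** Excluding 10%, 20% or 30% of the 40 controls gives 78.1%, 75.4% or 72.1% power at 0.28. In the worst cell above, where about 31% overlap, keeping them gives 77.1% at 25% carry-over and 73.7% even at 50%. Excluding late controls also removes those closest in calendar time to the mFI-Care group.

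**The case for a change.** The strongest case for a change is that the text permits overlap, control teaching is done by the staff being trained, and the inservice for physicians, therapists and social workers has neither a volunteer restriction nor a stated start. The reassurance about size rests on one unsourced carry-over figure, and the table shows 66.2% power at the far corner. Changing the trigger takes one sentence, and recording the training dates with a count of controls still present costs almost nothing.

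The reading of the text stands, and so does the point that the size cannot be fixed from the documents. The far corner, however, needs every overlapping control to receive the whole effect while exposed. That does not fit a plan that describes curriculum, rounds reporting, peer support and full app access for mFI-Care parents only. The sentence is short, but the pause it imposes is not cheap. If the study end can move, enrolment is protected, but the calendar gap between groups still widens. Secular change can bias the result in either direction, whereas dilution only weakens a real effect.

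Recording dates and counting infants is good housekeeping, but with no analysis attached it alters no result. An analyst who wants to check late controls can use ordinary admission, discharge and training dates. Control parents already track time learning from nurses and caregiving time, so drift near the end of the control phase can be examined. For the staff comparison, the natural reading of measures taken during the control condition is that they precede training.

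**Conclusion.** The plan leaves a short window in which late controls may meet trained staff, and no change is needed. With 25% carry-over and no lag, the loss is 0.003-0.011 on a difference of 0.28, or 1 to 3 points of power. A two-week lag roughly halves the loss in the long-overlap case or better. Larger losses need higher carry-over, down to 66.2% power at the extreme, and the documents neither confirm nor exclude the values in between. Against this, waiting for the last control costs about 4-14 weeks. With a fixed end, about 9-59 admissions are missed and the required enrolment share rises from 44% to 48-93%, and in either case the calendar gap widens. No net gain has been shown. These sizes rest on the assumed enrolment length, stay, lag, carry-over, outcome period and spread of stays; only the SD, sample size, alpha and admissions come from the plan.

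### The primary t-test of sequential groups is unadjusted and in effect limited to infants with endpoint weights; adjustment for baseline weight Z-score and GA should be prespecified rather than optional

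*Combined protocol and SAP*

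**What the plan says.** All of the analysis text is in the Statistical Analysis Plan section.

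- **Population:** "Data analysis will be based on an intention-to-treat strategy with all participants enrolled in the usual FCC or mFI-Care groups" at UCSF. The rest of that sentence concerns compliance: participants stay in their own group whatever they actually did.
- **Primary comparison:** "Outcomes will be compared between the usual FCC and mFI-Care groups using t-tests for continuous variables". The primary outcome is change in weight Z-score. The two time points are not stated.
- **Expected loss:** "Assuming 20% attrition, we will have complete data on 40 infants per group", from 50 enrolled per group.
- **Adjustment:** "Variables that differ among the groups may be considered as covariates when examining group differences in the primary and secondary outcomes". GA and birth weight are the named examples of potential confounders. The SAP adds: "The covariate-adjusted scores may provide more precise estimates of the effect sizes".
- **Group formation:** under mFI-Care Group in the Study Protocol, staff are trained after usual FCC enrolment has finished. Then: "Once training and inservice education are complete, mFI-Care enrollment will commence". No randomisation is described.

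No sentence says what happens to an infant who has no endpoint weight.

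**The concern.** A t-test on a change score uses only infants with both weights, so the infants without an endpoint weight leave the primary analysis without any stated rule. The groups come from different calendar periods and are not randomised, so baseline weight and GA may differ between them. The infants who are lost may also differ from those who remain.

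Adjustment for baseline would deal with the part of both problems that baseline explains. The plan leaves it to a choice made after seeing which variables differ. A covariate that predicts growth or loss can be passed over because the enrolled groups look alike on it.

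What is at stake is the primary estimate and its confidence interval, which the SAP intends to use in planning the future US cRCT.

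**Working it through.** **Inputs from the SAP:** 50 enrolled and 40 complete per group, SD 0.44-0.47, two-sided alpha 0.05, 80% power, detectable difference 0.28-0.29.

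**Assumed, because the documents give no figures:** SD 0.455 (the midpoint), correlation between baseline weight Z-score and its change of -0.3 to -0.5, no true effect.

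**1. The plan's own figure.** Enrolment: 40/(1 - 0.20) = 50. Detectable difference = SD × √(2/40) × (1.960 + 0.842):

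- SD 0.44: 0.276
- SD 0.47: 0.294

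The exact t calculation gives 0.279 and 0.298. The stated 0.28-0.29 therefore reproduces at 40 per group. At 50 per group the normal formula would give 0.247-0.263. The power rests on infants with complete data, which is a correct allowance for attrition.

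**2. Precision.** Unadjusted SE = 0.455 × √(2/40) = 0.102. Adjusting for a covariate with correlation r multiplies this by √(1 - r²):

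- r = 0.3: 0.102 × 0.954 = 0.097
- r = 0.5: 0.102 × 0.866 = 0.088

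Simulation of the regression on observed infants at 20% loss gives 0.089-0.098, against about 0.101 unadjusted.

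**3. Baseline difference.** If the groups differ by 0.3 SD at baseline (assumed), the unadjusted difference moves by 0.3 × |r| × SD:

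- r = 0.3: 0.3 × 0.3 × 0.455 = 0.041 Z
- r = 0.5: 0.3 × 0.5 × 0.455 = 0.068 Z

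The SAP does not say how a difference is judged. If it were judged by a 5% test, an observed 0.3 SD difference with 50 per group gives t = 0.3 × √(50/2) = 1.5. That is below the critical value of about 1.98, so the covariate could be left out.

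**4. Loss that depends on baseline.** Simulation with 50 per group and 10,000 runs per case. Loss in mFI-Care depends on baseline Z (log-odds slope 0.7 or 1.4 per SD); loss in FCC is random. GA was not simulated. Reversing the slope reverses the sign.

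| Case | t-test: bias (Z) | t-test: rejection | Adjusted: bias (Z) | Adjusted: rejection |
|---|---|---|---|---|
| 20% loss, one group dependent | 0.02-0.05 | 5-8% | within 0.003 | about 5% |
| 10% loss, one group dependent | 0.01-0.03 | 5-6% | within 0.002 | about 5% |
| 20% loss, same dependence in both | within 0.002 | about 5% | within 0.002 | about 5% |

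**5. Limit of adjustment.** If 20% loss in one group depends on the part of the change that baseline does not explain, bias is 0.05-0.09 Z with or without adjustment. Rejection is 8-17%.

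**6. What a shift analysis would show.** Suppose the observed difference equals the plan's detectable difference and 20% are missing in one group. The mean change of those missing infants must then differ from the observed mean by (difference - CI half-width)/0.20 before the interval reaches zero:

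- SD 0.44: (0.28 - 0.196)/0.20 = 0.42 Z
- SD 0.47: (0.29 - 0.209)/0.20 = 0.40 Z

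At 10% missing the figure is 0.93-0.96 Z.

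**The case against.** The case against is substantial.

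- **The consequence is not demonstrated.** The SAP does not define attrition. Complete data may include App or parent-reported items, so fewer than 20% of endpoint weights may be missing. This stands.
- **The repairable bias is small.** It is 0.02-0.05 Z against an SE of about 0.10, and the top of that range needs strong dependence in one group and none in the other. With half the dependence in the other group, bias falls to 0.008-0.021 Z. This stands and limits the severity.
- **Regression on observed infants is still a complete-case analysis.** True. It removes bias only from loss explained by the covariates. The larger biases in step 5 of the working remain.
- **Adjustment can itself move the estimate.** With a 0.3 SD baseline difference the adjusted and unadjusted results part by 0.04-0.07 Z. That is correct, but if baseline Z is a confounder, as the SAP treats birth weight, the unadjusted result is the one in error. The divergence is a reason to report both.
- **The SAP already allows adjustment.** It does, but it neither names the model nor commits to it. Optional use after inspection does not guarantee the protection or the precision.

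A reader might also infer that heavier documentation in mFI-Care produces unequal loss, since there "mFI-Care parents will be expected to document time spent with their infant and record infant activity, feeds and output using the We3Health App" while in usual FCC "Parents will not be asked to formally document any observations of their infant or their own skills acquisition". The documents do not support this. Usual FCC parents also track time and keep a journal in the same App, and nothing links parental documentation to a missing infant weight.

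**Conclusion.** The point holds as a choice of analysis. For sequential, non-randomised groups, a prespecified regression on baseline weight Z-score and GA is a better primary analysis than an unadjusted t-test with discretionary adjustment. Under the assumed correlations it cuts the SE from about 0.101 to 0.089-0.098. It also removes illustrative biases of 0.02-0.05 Z (baseline-dependent 20% loss in one group) and 0.04-0.07 Z (0.3 SD baseline difference). Bias from loss is less if loss is lower or similar in both groups. The true size and direction in this trial cannot be known from the documents.

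Three stronger readings are not supported:

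- **That the sample size is wrong.** The attrition allowance and the detectable difference both reproduce.
- **That the primary result will be materially biased by missing weights, or the future cRCT misdirected.** Neither the amount of missing weight data nor its pattern by group is given.
- **That multiple imputation is needed.** With the same covariates, simulation gave results equal to the regression (SE 0.090-0.099, bias within 0.002 Z).

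Severity is minor to moderate.

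**What to change.** 1. Make the primary estimate the between-group difference, with its confidence interval, from a linear regression of change in weight Z-score on group, baseline weight Z-score and GA. Prespecify it whether or not these variables differ between groups.
2. Report the unadjusted t-test as secondary, so that any divergence is visible.
3. Report the number of missing endpoint weights and the reasons by group, with death and transfer kept separate. Use weights already in the hospital record, where available, unless consent is withdrawn. The documents do not say that endpoint weights are in that record.
4. Optional: shift the assumed mean change of missing infants by group, in either direction, until the conclusion changes. Only this step addresses loss unrelated to baseline.
5. Leave the 40-per-group power statement as it is.

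The cost is a few SAP sentences, one regression and a little data extraction, with no extra infants. The downsides are that the adjusted estimate relies on loss being explained by the covariates, and that in non-randomised groups the two estimates may disagree and need explaining.

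### Does naming four sites but analysing only UCSF leave the group comparison undefined?

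*Combined protocol and SAP*

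**What the plan says.** The Study Protocol opens with "Study staff at UCSF, UCLA, BCH-O, and CRMC will perform the following procedures" and then describes usual FCC and mFI-Care. Under the heading on mFI-Care clinical team and alumni parent training, the two groups are sequential: "After completion of the usual FCC group enrollment, nurses who volunteer to provide care to mFI-Care infants/parents" are trained, and mFI-Care enrolment starts once training is done. Under Parent Resources for both groups the text turns to one hospital: "Each single patient room in the study site provides a reclining chair".

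The Statistical Analysis Plan makes these statements, in this order:

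- The analysis follows intention to treat, with "all participants enrolled in the usual FCC or mFI-Care groups at UCSF analyzed within their respective groups".
- The tests come next: "Outcomes will be compared between the usual FCC and mFI-Care groups using t-tests for continuous variables", with Wilcoxon and chi-square tests for ordinal and categorical outcomes. No site term is named.
- The investigators "anticipate enrolling 50 parent-infant pairs in each group (usual FCC and mFI-Care) at UCSF", and 20% attrition leaves 40 per group.
- "Enrollment at the UCLA site is exploratory to further assess feasibility and acceptability thus statistical power is based on the UCSF sample".
- For the primary outcome, change in weight Z-score, "we will have 80% power to identify a group difference of 0.28-0.29".

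Variables that differ between groups may be used as covariates; site is not among the examples. BCH-O and CRMC do not appear in the SAP.

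**The concern.** Four hospitals are named as carrying out the procedures and only one is named as being analysed. The sentence that lists the tests carries no site restriction of its own. Taken alone, it would allow all four hospitals to be pooled in simple two-group tests.

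That would matter because mFI-Care enrolment follows FCC enrolment. If hospitals joined at different times, the mix of sites could differ between the groups, and an unadjusted comparison would carry differences between hospitals into the estimated effect. The covariate rule is optional and depends on the data, so it would not reliably remove them.

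If other hospitals' outcomes are instead left out, any weight Z-scores collected there add nothing to the confidence interval that the SAP wants for planning a later cluster trial. A choice left open until data are seen also allows selective pooling.

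**Working it through.** **1. Which sample does the power statement describe?** Inputs from the SAP: 40 per group, SD 0.44-0.47, two-sided alpha 0.05, power 80%.

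Detectable difference = SD × (1.960 + 0.842) × √(2/40) = SD × 0.626.

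- SD 0.44: 0.276
- SD 0.47: 0.294

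These round to the stated 0.28-0.29. The noncentral t gives 0.279-0.298, so the upper end would round to 0.30, a trivial difference. Attrition also agrees: 50 × 0.80 = 40. With 50 completers per group (an assumed 10 extra per group from elsewhere) the noncentral t gives 0.249-0.266, which is not what the SAP states. The powered t-test is the UCSF t-test.

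**2. Do the SAP's sentences conflict?** The population sentence limits the analysis to UCSF. The next sentence names the tests and the one after returns to UCSF admissions and the UCSF target. The UCLA sentence then explains why power rests on UCSF. Only by lifting the test sentence out of this run can it be read as covering four hospitals. The singular study site under Parent Resources describes rooms and family facilities and does not bear on the analysis population.

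**3. What would harm from pooling require?** With no site term, and a common difference between the other hospitals and UCSF:

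bias = (share of other-site infants in mFI-Care − share in FCC) × hospital difference in mean Z-score.

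The documents give no figure for any of these, so the following are assumptions added to 40 + 40 at UCSF.

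- Other sites add 10 FCC and 10 mFI-Care: shares 0.20 and 0.20, bias 0.
- Other sites add 0 FCC and 20 mFI-Care: shares 0 and 20/60 = 0.333. A hospital difference of 0.1-0.3 Z gives bias 0.033-0.100.

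The second case needs pooling, no site term, enrolment elsewhere in one phase only, and a sizeable hospital difference, all at once. The SAP plans no such analysis.

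**4. What would a supportive site-adjusted model gain?** For a linear model with group and site as fixed effects:

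SE = SD × √(1/Σ[n₁n₂/(n₁+n₂)]), summed over sites, with N − sites − 1 degrees of freedom.

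- UCSF alone: 40×40/80 = 20, so SE = 0.224 × SD and the 95% half-width is 0.196-0.209.
- 10 extra per group, split 4, 3 and 3 over three hospitals: 20 + 2 + 1.5 + 1.5 = 25, so SE = 0.200 × SD and the half-width is 0.175-0.187 (about 11% narrower).
- 5 extra per group (2, 2, 1): sum 22.5, half-width 0.184-0.197 (about 6%).
- 20 extra per group (7, 7, 6): sum 30, half-width 0.159-0.170 (about 19%).
- Other sites in one phase only: n₁n₂ = 0 at each, so they add nothing.

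These intervals describe the enrolling hospitals only. If the true effect varied between hospitals with an assumed SD of 0.10, the half-width for an average over hospitals would be 0.275-0.284 from UCSF alone and 0.234-0.243 with 10 extra per group.

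**The case for a change.** The strongest case for a change is that the UCSF restriction on the test sentence is implied rather than written, and that two of the four named hospitals have no stated role at all. Calling UCLA exploratory explains the basis for power but gives no rule for its outcome data. A few sentences would settle the matter before comparative data are seen, and one supportive model would use any extra data at no cost in patients.

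Part of this stands. The SAP does not say whether BCH-O and CRMC enrol pairs, and for UCLA it states enrolment but not its number, phase or outcomes. That is missing detail about sites outside the comparison; it does not alter the comparison.

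The case for the supportive model is weaker. Its gain depends on undocumented enrolment in both phases and on weight Z-scores being collected elsewhere, and it may be nil. In the illustrations each extra hospital holds 1 to 7 infants per group, and stratified rank or categorical tests on strata that small would add little. Bringing UCLA into a comparative model also goes beyond the role the SAP gives it. Nor would site adjustment remove a time trend: the contrast between successive phases stays before-after.

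**Conclusion.** The concern does not call for a change. Followed as written, the plan gives a UCSF-only intention-to-treat comparison, a legitimate choice whose stated power reproduces at 40 per group (0.276-0.294 against 0.28-0.29). Nothing in the site wording is shown to bias that comparison.

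The possible bias from pooling, 0 to 0.100 Z in the two illustrated splits, belongs to an analysis the SAP does not plan and rests wholly on assumed enrolment and assumed hospital differences. The possible gain in precision, from nothing to about 19% in half-width, rests on assumed completers elsewhere and, for the fixed-effect interval, on describing the enrolling hospitals only.

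What remains is a gap in describing the other sites, and sensible analysts will fill it: the UCSF comparison is the main result, UCLA is reported as exploratory, and any BCH-O or CRMC data are described separately. This rests on reading the SAP's population, target and power sentences together, which is how they are set out.

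### Is the stated detectable difference of 0.28-0.29 wrong because the t-test at SD 0.47 needs 0.30?

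*Combined protocol and SAP*

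**What the plan says.** All the relevant text is in the Statistical Analysis Plan section of the combined document. The investigators "anticipate enrolling 50 parent-infant pairs in each group (usual FCC and mFI-Care) at UCSF". They then write: "Assuming 20% attrition, we will have complete data on 40 infants per group". UCLA enrolment is exploratory, and "statistical power is based on the UCSF sample".

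On variability: "The primary outcome, change in weight Z-score, typically has a standard deviation of between 0.44-0.47". The range is attributed to an earlier pilot and a Canadian-led cluster trial. The power statement opens "With a 0.05 null-hypothesis rejection threshold (alpha) for the two-tailed t-test" and concludes that "we will have 80% power to identify a group difference of 0.28-0.29".

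The section does not say whether the power figure came from a normal approximation or from the noncentral t distribution. It also names no minimum important difference for the primary outcome.

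**The concern.** The power sentence refers to a two-tailed t-test, so a careful reader will check it with the noncentral t distribution. On that check the lower end agrees and the upper end does not: at SD 0.47 the difference with 80% power is 0.298, which prints as 0.30. Put the other way, a true difference of 0.29 at SD 0.47 has 77.8% power, and 43 complete infants per group would be needed to reach 80%.

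This is the only power statement in the document and it concerns the primary outcome. If it were a genuine miscalculation, the study's sensitivity would be overstated at the less favourable end of its own SD range.

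**Working it through.** **Inputs**, all from the Statistical Analysis Plan section:

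- Complete infants per group: 50 × (1 − 0.20) = 40
- SD: 0.44 to 0.47
- Alpha 0.05, two-sided; power 80%
- Two independent groups compared by t-test

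**Step 1: reproduce the plan's figure.** The usual formula is difference = (z for 0.975 + z for 0.80) × SD × √(2/n).

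- Multiplier: (1.960 + 0.842) × √(2/40) = 2.802 × 0.2236 = 0.6265
- SD 0.44: 0.6265 × 0.44 = 0.276, printed as 0.28
- SD 0.47: 0.6265 × 0.47 = 0.294, printed as 0.29

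Both ends match the SAP. Other readings do not: a one-sided test gives 0.245 to 0.261, and 50 per group gives about 0.25 to 0.27.

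**Step 2: exact t calculation.** With 78 degrees of freedom, the standardised difference giving 80% power is 0.6343.

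- SD 0.44: 0.6343 × 0.44 = 0.279, printed as 0.28
- SD 0.47: 0.6343 × 0.47 = 0.298, printed as 0.30

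| Difference | SD | Power, normal approximation | Power, exact t |
|---|---|---|---|
| 0.28 | 0.44 | 81.2% | 80.3% |
| 0.29 | 0.47 | 78.8% | 77.8% |
| 0.30 | 0.47 | not needed here | 80.5% |

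**Step 3: split the gap at the upper end.** The total is 0.298 − 0.290 = 0.008 Z-score units.

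- Choice of method: 0.298 − 0.294 = 0.004
- Rounding to two decimals: 0.294 − 0.290 = 0.004

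At the unrounded 0.294, exact-t power is 78.9%, about one point below 80%.

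**Step 4: compare the gap with the precision of the inputs.**

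- An SD of 0.465 also prints as 0.47. Under the exact t calculation it gives 0.6343 × 0.465 = 0.2949, which prints as 0.29.
- The exact t-test reaches 80% power at 0.29 whenever the SD is about 0.457 or less, and that value lies inside the stated range.
- The 40 completers are a forecast. At SD 0.47 and a difference of 0.29, exact-t power is 79.8% with 42 per group and 80.7% with 43. Forty-three completers from 50 enrolled means 7/50 = 14% attrition instead of the assumed 20%.

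**The case for a change.** The strongest counter-argument is that the sentence ties its 80% to a t-test and mentions no approximation, so it should be true of that test. Moreover, 0.29 falls short of 80% at SD 0.47 under either method: even the normal approximation gives 78.8%, because 0.294 was rounded down, and rounding a detectable difference down always flatters the power. The larger SD is also the cautious case, which is where a reader would want the claim to hold.

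The arithmetic in this argument is right. A statistician quoting the exact t result would write 0.28-0.30, and rounding upward would have been the more cautious convention. What it does not establish is an error. Planning a t-test with the normal formula is ordinary practice, and with 78 degrees of freedom the two methods differ by 0.004 at the upper end. Rounding both ends to the nearest second decimal suits an SD quoted to two decimals. The lower end of the range is correct under both methods.

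Nor does anything turn on the difference. The SAP starts from expected enrolment and reports what that number can detect; it does not work back from 0.29 to a sample size. It looks to confidence intervals around the group differences, not to this figure, to inform sampling for the later US trial.

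**Conclusion.** The concern does not hold. The printed range follows from the SAP's own inputs by a standard formula with ordinary rounding. The exact t calculation moves one endpoint by one unit in the second decimal, from 0.29 to 0.30, and puts power at 0.29 with SD 0.47 at 77.8%, 2.2 points below the stated 80%. That reflects a choice of approximation plus rounding, and it is smaller than the uncertainty in the SD and in the number of completers.

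This conclusion takes 40 analysable infants in each group, a common SD and the unadjusted two-group comparison as given. That the normal approximation was used is inferred from the match at both ends; the document does not say so. Had a target difference lain between 0.29 and 0.30, or had the sample size been derived from 0.29, the point would deserve a correction. Neither is the case, so enrolment, analysis and interpretation are unaffected.
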